9.6 Lost to Follow up

For studies conducted in the UK we will utilise the National Health Service (NHS) number to trace participants whom may have changed their General Practitioner if consent is provided for us to inform the general practitioner about the study. For the sub-study of infants followed up to 12 weeks of age, we will make two phone calls, one week apart, to the number given by the woman and one attempt to contact the family general practitioner. If following these calls there is no response, we will deem the infant lost to follow up.

9.7 Definition of the End of Trial

The study will have ended at the Last Patient Last Visit. We will notify the REC of the end of trial within 90 days of its planned completion or within 15 days if the study is terminated early.

10 Study Procedures

10.1 Screening assessments

All women who indicate an interest in the study will be assessed to ensure they meet the inclusion criteria before enrolment.

10.2. Baseline assessments

As above.

10.3. Study procedures

Delivery blood samples: Following oral confirmation of consent, blood will be obtained from the mother at any time during labour (or within 48 hours of delivery) and / or from the cord once the placenta has been delivered and when the obstetric/midwifery team deem it is safe to do so. 5mL of blood will be collected into a BD® serum separator tube. Blood samples will be transported to the laboratories to be processed and the serum collected into eppendorf tubes and frozen at - 20°C to -80°C for later processing.

Relevant clinical information will be extracted from the mothers hand-held or hospital notes onto the CRF. This will include: baby/ies' gestation at birth (wks), receipt of IAP (yes/no), type of IAP including dose and quantity (list), time between administration of first IAP and delivery (hours), recent blood transfusion (in last 1 month), elective c/s (yes/no).

Vaginal and rectal swabs: At Kingston and St George's Hospitals only, and for those who consent to participate in the colonisation study, a single rectovaginal swab (Copan swab) will be obtained at any time from 35 weeks gestation up to (and including) delivery, either by the study midwife or by the mother herself if she prefers (with appropriate written guidance). The swab is inserted into the lower half of the vagina and turned slowly clockwise once before removing and inserting past the anal sphincter into the low rectum. If there is any resistance to insertion the procedure should be abandoned. The swab is then inserted into a sterile Amiens media tube and transported to the local clinical laboratory for processing according to standard methods. The result (positive / negative) will then be entered into the maternal notes and the mother informed by phone (if GBS positive) and by letter (if positive or negative). It is anticipated that women will subsequently be managed according to the relevant Royal College of Obstetrics and Gynaecology Greentop Guideline on GBS with regard to the swab result – if positive the mother would be offered IAP (https://www.rcog.org.uk/en/guidelines-research-services/guidelines/gtg36/).

Collection of infant blood: *At Kingston and St George's Hospitals only*, and only in those women who are participating in both the delivery blood collection study and the colonisation study and who are shown to be colonised, they will also be invited to participate in the infant antibody kinetics sub-study. In this sub-study babies born to colonised mothers will be randomized to have one blood sample obtained, at 4, 8 or 12 weeks of age. This will be undertaken by suitably trained research nurses or doctors using venipuncture or capillary sampling (2 ml) and then blood will be processed and stored as described above.

Collection of Guthrie cards: *At Kingston and St George's Hospitals only*, and only in those women who are participating in both the delivery blood collection study and the colonisation study, they will also be invited to participate in the infant Guthrie card collection sub-study. In this sub-study mothers will be asked for permission to obtain a sample of the Guthrie card, which is obtained routinely in all babies at around 5 days of age. This will be obtained from the National Screening Laboratory and stored for antibody analysis.

iGBS surveillance: Microbiologists and paediatricians at the 5 participating hospitals will be engaged at the start of the study and information provided about the study and its rationale. They will be asked to make contact with study staff should a case of iGBS occur (only up to 5 cases would be expected with the cohort of this feasibility study). Study staff will additionally make contact with each laboratory on a weekly basis to ensure that cases have not been missed. When a case of iGBS occurs, the relevant paediatrician will be contacted by the study team and asked to recruit the mother and baby to the iGBS sub-study. Following consent from the mother, a sample of blood will be obtained from her and from her baby and processed as above. She will also be asked to provide a single rectovaginal swab to be processed as above.

Follow-up of babies: A follow-up telephone call will be made to all parents 90 days after their babies birth to establish whether the infants developed iGBS disease during this time period. This phone call will be made by a member of the study team.

Subsequent assessments

As indicated, a follow-up telephone call will be made to parents 90 days after their baby/babies were born to confirm whether the infants developed iGBS disease during this time period. In the event of a case of iGBS occurring, the relevant paediatrician will be contacted by the study team and asked to recruit the mother and baby to the iGBS sub-study. Following consent from the mother a sample of blood will be obtained from her and from her baby by suitably trained research nurses or doctors and processed as above. She will also be asked to provide a single rectovaginal swab, either taken by the midwife or mother herself, to be processed as above.

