From a global perspective the burden of iGBS in pregnant women and young infants has recently been quantified and shown to be a major problem ⁶. From a UK perspective we have recently seen an increasing burden of disease, despite a national (risk-based) policy for IAP ¹⁰, and the UK National Screening Committee has recently recommended not to introduce an (arguably more effective) national screening program (https://www.gov.uk/government/news/screening-pregnant-women-for-gbs-not-recommended) - although the clinical and cost effectiveness of screening for GBS in pregnancy is the objective of another HTA application (17/86). Conversely, the UK population has widely accepted the concept of maternal vaccination, with high coverage of maternal pertussis vaccination (>70%) and the first (ever) demonstration of its effectiveness ²³. The UK is therefore in an excellent position to pursue the development, licensure and implementation of a maternal vaccine against GBS.

Licensure and policy decisions for a candidate GBS vaccine would be significantly accelerated if an immune marker was established as a correlate of protection. Regulatory bodies, including the European Medicines Agency and the Food and Drug Administration ²⁴, have made it clear that they would now consider this approach to licensure if robust evidence can be developed. Additionally, the Joint Committee on Vaccination and Immunisation has indicated it would consider a recommendation for routine implementation of a vaccine licensed on the basis of correlates - as it has for other recent vaccines (meningococcal C ¹⁷ and meningococcal B).

The two critical gaps that have to be filled to make decisions on the use of such vaccines (both at the regulatory and recommending body level) are: (i) the development of a standardised immunoassay to measure antibody levels that act as the correlates of natural immunity, supported by measurement of functional antibody assays, and (ii) a large biobank of sera to establish the correlate using these new standardised assays. The first of these gaps is being addressed by a consortium of groups from academia, public health, and industry (lead by co-applicant KLD), and the second is the basis of this study.

Given the anticipated size and logistical complexities of a serocorrelates study that would be needed to address this, the aim of this initial feasibility study is to test key operational aspects of the study design.

5 Study objectives

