5.2. Secondary objectives

To test the key operational aspects for a proposed large serocorrelates study:

- enrolment rate (the rate (proportion) of eligible women who are willing to participate in the delivery blood collection study)

- maternal and / or cord blood collection rate

key clinical exclusion data (gestation at birth, receipt of IAP in labour (yes/no), type of IAP (list), time between administration of IAP and delivery (in hours)) collection rate
 infant iGBS surveillance consent rate

In a sub-study of the main study above to assess:

- rectovaginal swab study consent rate
- rectovaginal swab collection rate
- rectovaginal GBS colonisation rate
- rectovaginal GBS CPS serotype-specific colonisation rates

-

In the sub-study above where samples of maternal/cord blood and rectovaginal swabs are available to assess:

- infant blood sample study consent rate
- infant Guthrie card consent rate
- infant Guthrie card collection rate

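### The swab window runs through labour with no link to the start of intrapartum antibiotics, and swab time is not a listed CRF item, so post-antibiotic negatives cannot be identified and could lower the colonisation rates

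*Protocol*

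**What the plan says.** Section 10.3 (Vaginal and rectal swabs) provides for one rectovaginal swab per woman at two hospitals, which "will be obtained at any time from 35 weeks gestation up to (and including) delivery". Scoring has two outcomes: "The result (positive / negative) will then be entered into the maternal notes". The woman is then told, and it is anticipated that a positive woman would be offered IAP.

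Section 5.2 makes two rates from this swab secondary objectives: "rectovaginal GBS colonisation rate" and "rectovaginal GBS CPS serotype-specific colonisation rates". Section 14.3.1 says the proportions achieved on the study endpoints will feed the sample size of the main study.

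Sections 10.3 (Delivery blood samples) and 12.2 list the clinical items for the CRF. They cover gestation, IAP receipt and type, the hours from first IAP to delivery, and recent transfusion; Section 10.3 adds elective caesarean. Neither list names the date or time of the swab. Section 4 (Study Rationale) describes the setting as one of rising disease "despite a national (risk-based) policy for IAP", so IAP can be started for risk factors without a swab result.

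Section 10.3 (Collection of infant blood) takes only women "who are shown to be colonised, they will also be invited to participate in the infant antibody kinetics sub-study".

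**The concern.** With one swab, two possible results and a window that includes labour, a woman can start IAP for a risk factor and be swabbed hours later. If antibiotics suppress growth, a carrier is recorded as negative and yields no isolate to serotype. There is no second swab to correct this and no indeterminate category. The error goes one way, and recruiting more women does not shrink it.

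This reaches the data capture as well as the analysis. An analysis plan can set a rule for post-IAP swabs only if it can find them, and the listed items time IAP against delivery, not against the swab.

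At stake is the use of these rates for planning. Section 4 defines both cases and controls of the main study by exposure through maternal colonisation, so an underestimate would understate the number of usable controls.

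**Working it through.** **The plan's own figure.** Section 14.3.1 gives 1000 of 3600 eligible women as 28%: 1000/3600 = 27.8%, which agrees. The protocol states no precision for the colonisation rate.

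**Inputs from the protocol.** True colonisation 20% (Section 4); 1000 swabs (Section 14.3.1).

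**Assumed inputs (the protocol gives none of these).**
- f, the share of swabs taken after IAP has started: 5%, 10% or 20%.
- p, true colonisation among those women: 20% or 40%.
- l, the share of carriers among them whose swab turns negative: 50% or 90%.

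That antibiotics reduce culture yield is a general mechanism and is not stated in the protocol.

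**Sampling error.** 1.96 × √(0.20 × 0.80 / 1000) = 0.0248, or ±2.5 points.

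**Expected observed rate** = 0.20 − f·p·l:

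| f | p=20%, l=50% | p=20%, l=90% | p=40%, l=50% | p=40%, l=90% |
|---|---|---|---|---|
| 5% | 19.5% | 19.1% | 19.0% | 18.2% |
| 10% | 19.0% | 18.2% | 18.0% | 16.4% |
| 20% | 18.0% | 16.4% | 16.0% | 12.8% |

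At f = 10% the loss is 1.0 to 3.6 points, or 10 to 36 carriers per 1000 swabs against about 200 true carriers. The loss exceeds 2.48 points in 4 of the 12 cells, and in none at f = 5%.

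**When it is negligible.** With equal colonisation in both groups (p = 20%) the loss is 0.20·f·l. At f = 2% it is at most 0.20 × 0.02 × 1 = 0.4 points. It equals the whole half-width only when f·l = 0.0248/0.20 = 12.4%. A smaller loss still matters to the interval: in this model a nominal 95% interval covers the truth about 87% of the time at f·l = 5% and 62% at 10%.

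**Would a pre-IAP-only rate repair it?** Its expected value is (0.20 − f·p)/(1 − f). With p = 20% it is 20%. With p = 40%:
- f = 10%: (0.20 − 0.04)/0.90 = 17.8%, against 18.0% (l = 50%) or 16.4% (l = 90%) if nothing is changed.
- f = 20%: (0.20 − 0.08)/0.80 = 15.0%, against 16.0% or 12.8%.

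So if women swabbed after IAP are more often colonised, restriction does not recover 20%, and at l = 50% it is further from it than no change.

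**Precision of the pre-IAP stratum.** With 10% set aside, 1.96 × √(0.16/900) = 0.0261, or ±2.6 points.

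**Bounds on the overall rate.** The lower bound counts post-IAP negatives as not colonised, the upper as colonised. At f = 10%, p = 20%, l = 50%, 100 swabs are post-IAP and 20 × 0.5 = 10 of them are positive, leaving 90 negative. The bounds are 19.0% and 19.0% + 9.0% = 28.0%. At f = 2% they cannot be more than 2 points apart.

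**The case against.** The strongest reply is that Section 10.3 sets a collection window and does not say which swabs enter the rate. That rule is commonly left to an analysis plan, which is not at hand. The CRF lists are also open-ended, so swab time may be captured elsewhere. This stands in part. A reader might infer that the protocol counts every swab, or that swab time will not be recorded; it states neither. What remains is that the window admits post-IAP swabs and the listed items would not identify them.

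Second, swabbing looks mainly antenatal. Entering the result, telling the woman and then offering IAP fits a swab taken before labour. This stands, and it points to a small f, though swabs at delivery are expressly allowed.

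Third, a reader might infer that colonised women given IAP are lost to the infant sub-study. The protocol does not support that. A woman whose swab was positive before IAP remains eligible after receiving it, and she is already counted correctly. Only a carrier first swabbed after IAP and found negative would be missed. The infant-blood objective in Section 5.2 is a consent rate, and no bias in it is shown.

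Fourth, these are descriptive secondary objectives in a feasibility study whose primary aim is serum collection. That limits the weight of the point, but not the case for a nearly free correction.

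**Conclusion.** The concern holds as a gap in measurement. Swabs taken after IAP are permitted, their negatives cannot be identified from the listed data, and any resulting error lowers the colonisation and serotype-specific rates.

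A reader might go further and conclude that the rates will be materially biased. The documents do not support that, because the share of post-IAP swabs, colonisation in those women and the loss of culture yield are all assumed. Under the ranges above the loss runs from 0.5 to 7.2 points, and at 10% post-IAP swabs from about 1 to 3.6. It exceeds the ±2.5 point sampling error only toward the upper end and is at most 0.4 points if 2% of swabs follow IAP and colonisation is equal in both groups. Without swab timing, the sponsor could not show which of these applies.

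**What to change.** Add swab date and time to the CRF, and confirm that delivery date and time are captured. The start of IAP then follows from delivery time minus the recorded interval from first IAP to delivery, and each swab can be classed as before or after it.

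Report the colonisation and serotype-specific rates overall and separately for pre-IAP and post-IAP swabs. Treat a post-IAP negative as indeterminate, for example by giving lower and upper bounds on the overall rate.

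Two shortcuts should be avoided. The pre-IAP-only rate should not be the sole estimate, because women swabbed after IAP may differ in colonisation. Nor should all IAP recipients be excluded: swab-positive women are offered IAP because of their result, so this would remove true positives and lower the rate further.

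The cost is one extra field, one extra table and a slightly less precise pre-IAP estimate (±2.6 points if 10% are set aside). The bounds will be wide if many swabs follow IAP, which reflects what the data can support. The change concerns measurement and reporting only, not who receives antibiotics.

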10.4. Summary flow chart of study assessments

See previous flow chart

10.5. Methods

10.5.1. Laboratory procedures

Swab microbiological testing: The swab will be sent to the microbiology laboratory for processing according to United Kingdom Accreditation Services accredited methods for the testing of Group B Streptococcus from rectovaginal swabs.

Antibody testing: in a sub-study of samples from the swab / delivery blood sub-study, the impact of timing of processing of delivery blood sample storage conditions on serotype-specific GBS anti-CPS IgG concentrations will be assessed. 100 blood samples (samples where there is sufficient blood) will be divided further in order to assess the effect on anti-GBS concentrations of: 1. Different times between sample collection and sample processing (6 hours / 10 hours / 18 hours / 24 hours / 48 hours / 72 hours / 5 days / 7 days); 2. Different times between serum processing and serum freezing (24 hours / 48 hours / 72 hours / 5 days / 7 days).

Antibodies to GBS will be quantified using a multiplex ELISA and a opsonophagocytosis killing assay at St George's University of London laboratories using the standardized assays that are currently being established as part of a Gates Foundation funded collaboration led by a co-applicant (KLD). It is expected that these will be in place before the end of 2018.

10.5.2. Radiology or any other procedure(s) N/A

11. Safety Reporting

11.1. Definitions

Adverse Event (AE)— any untoward medical occurrence in a participant whether it is considered to be related to the intervention or not, that includes a clinical sign, symptom, or condition and /or an observation of a near incident such as incorrect dosing of antibiotics. (This does not include preexisting conditions recorded as such at baseline).

Serious Adverse Event (SAE)— any Adverse Event or untoward medical occurrence in a trial participant that can be wholly or partly to the intervention that resulted in any of the following:

- Results in death; or
- Is life-threatening (places the subject, in the view of the Investigator, at immediate risk of death)
- Requires hospitalisation or prolongation of existing hospitalisation (hospitalisation is defined as an inpatient admission, regardless of length of stay; even if it is a precautionary measure for observation; including hospitalisation for an elective procedure, for a pre-existing condition)
- Results in persistent or significant disability or incapacity (substantial disruption of one's ability to conduct normal life functions)
- Consists of a congenital anomaly or birth defect (in offspring of subjects or their parents receiving the trial intervention regardless of time of diagnosis).
- Or is another important medical condition

Important medical events that may not be immediately life-threatening or result in death or hospitalisation but may jeopardise the subject or may require intervention to prevent one of the outcomes listed in the definition of serious will also be considered serious.

11.2. Investigator responsibilities relating to safety reporting

Collection, recording and reporting of AEs (including serious and non-serious events and reactions) to the Sponsor will be done according to the Sponsor's Safety reporting for clinical studies Standard Operating Procedure (SOP) JREOSOP0033.

All AEs whether serious or not will be recorded in the hospital notes in the first instance. A record must also be kept in the participant's CRF and the Sponsor's AE Log JREOLOG0007. The AE log will be sent to the Sponsor on request and every 2 months.

All SAEs will be reported both to the Sponsor via the JREO & REC using the SAE report form for research other than CTIMPs (non-CTIMPs) published on the HRA website The Chief or Principal Investigator at any participating site will complete the SAE form which will be faxed both to the JREO on [name] or E-mailed to [contact], within 48hrs of the Investigator becoming aware of the event, and via email to the relevant REC.

The CI or PI will respond to any SAE queries raised by the Sponsor as soon as possible. Follow up reports must continually be completed within acceptable time-frames and sent as detailed above until the reportable event is considered resolved.

11.3. Notification of deaths

Only deaths that are assessed to be caused by the trial intervention will be reported to the Sponsor. This report will be immediate or within 24 hours of first knowledge.

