6.2. Treatment/intervention plan and rationale

No treatment / intervention planned as part of this feasibility study

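### Expedited reporting of SAEs and deaths depends on a trial intervention that the protocol says does not exist, and the scope of death reporting contradicts itself

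*Protocol*

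**What the plan says.** Section 6.2 of the protocol: "No treatment / intervention planned as part of this feasibility study".

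Section 11.1 defines an adverse event without regard to cause: "any untoward medical occurrence in a participant whether it is considered to be related to the intervention or not". It then narrows a serious adverse event by cause: "any Adverse Event or untoward medical occurrence in a trial participant that can be wholly or partly to the intervention". The verb is missing; the evident sense is attributable. A closing sentence, which carries no causal condition, adds that certain important medical events also count as serious.

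Section 11.2 sets two routes:
- All adverse events, serious or not, go into the hospital notes, the CRF and the Sponsor's log. The log reaches the Sponsor when asked for and at two-month intervals.
- For serious events, "All SAEs will be reported both to the Sponsor via the JREO & REC", and the form is due "within 48hrs of the Investigator becoming aware of the event".

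Section 11.3 adds a rule for deaths: "Only deaths that are assessed to be caused by the trial intervention will be reported to the Sponsor". On timing: "This report will be immediate or within 24 hours of first knowledge".

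**The concern.** Two of the three reporting routes turn on an intervention that the study does not have. It does, however, do things to participants. Section 10.3 describes maternal blood sampling in labour or soon after delivery, cord blood sampling, a rectovaginal swab at two hospitals, and a 2 ml infant sample by venepuncture or capillary puncture. An investigator who sees a serious event after one of these has to decide whether it is attributable to the intervention, and the protocol gives no usable answer.

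At stake is prompt notice of harm from study procedures to the Sponsor and the REC. Section 9.4 lists an unacceptable adverse event among the reasons for which a participant may withdraw or the study may stop early. That provision works only if such events are seen in time.

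**Working it through.** The protocol gives no figure to reproduce, so the check sets the provisions side by side.

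**Step 1. Routes, read literally with no intervention (Section 6.2)**

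| Route | Condition on cause | Recipient | Time limit | What qualifies |
|---|---|---|---|---|
| Death notification (11.3) | Caused by the trial intervention | Sponsor | Immediate or 24 h | Nothing |
| SAE report (11.1, 11.2) | Attributable in whole or part to the intervention; no condition in the sentence on important medical events | Sponsor and REC | 48 h from awareness | Only events under that sentence |
| Adverse event log (11.1, 11.2) | None | Sponsor | When asked for, and every 2 months | All adverse events, serious ones included |

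The unconditioned sentence describes events that may fall short of death, immediate threat to life or hospitalisation. It keeps part of the SAE route open but does not clearly bring deaths into it.

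**Step 2. What is lost.** For most serious events the surviving route is the log. Taking a month as 30 days, the longest scheduled gap is 2 × 30 = 60 days, against 48 h = 2 days, so up to 60 / 2 = 30 times as long unless the Sponsor asks sooner. Over the 4-month study period in Section 14.3.1, a two-monthly schedule gives 4 / 2 = 2 routine transmissions. The log goes to the Sponsor only. The REC does receive an annual progress report (11.4) and an end-of-study report (17), but the protocol does not say that either lists serious events.

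**Step 3. Does a generous reading cure it?** Suppose the intervention means the study procedures. Deaths then fall into three classes:

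| Death is | SAE report (11.1, 11.2) | Notification (11.3) | Log (11.2) |
|---|---|---|---|
| Caused by a procedure | Yes, Sponsor and REC | Yes, Sponsor | Yes, Sponsor |
| Partly attributable | Yes, Sponsor and REC | No, if caused is narrower than partly attributable | Yes, Sponsor |
| Unrelated | No | No | Yes, Sponsor |

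The first row is consistent. In the second, 11.2 sends the death to the Sponsor while 11.3, through the word only, says it is not reported. In the third, the log carries the death to the Sponsor while 11.3 again excludes it. The generous reading removes the emptiness but leaves the contradiction on scope.

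**Step 4. Time limits.** The SAE limit is 48 h and the death limit 24 h. A death reported within 24 h also meets 48 h, so the limits can coexist. They are simply not cross-referenced.

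**The case against.** The strongest defence is that this is loose template wording. Section 11.2 refers to the Sponsor's safety reporting procedure, which is not at hand, and uses the REC form for research other than medicinal-product trials. A sensible investigator would probably take the intervention to mean the blood sampling and swabs. Section 11.3 might also be meant as a rule for immediate notification only, in which case it would not clash with the SAE report or the log. Both readings are plausible, but neither is written down, and the word only points the other way.

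Three stronger readings may tempt a reader, and the document does not support them:

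- *No death or SAE would ever be reported, for any of about 4000 participants.* The log has no causal condition and takes serious events to the Sponsor, and the sentence on important medical events keeps part of the 48-hour route open. For deaths, 11.3 contradicts the log; that is an inconsistency to settle, not proof that nothing is reported.
- *The 24-hour and 48-hour limits conflict.* They do not (Step 4), and the reporting gap comes from the causality wording, not the limits.
- *Unreported infant deaths would be counted as loss to follow-up for invasive GBS disease.* This is speculative. Notifying the Sponsor is separate from what a site knows; cases are also sought through clinicians and weekly laboratory contact (10.3); and the loss-to-follow-up rule in 9.6 includes an attempt to reach the general practitioner and is written for the infant sub-study.

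**Conclusion.** The point holds as a defect in the safety-reporting text. As written, the death-notification rule in Section 11.3 is empty and the 48-hour SAE route is nearly so, because both refer to an intervention that Section 6.2 excludes. What is lost is expedited reporting to the Sponsor and most reporting of individual serious events to the REC; delayed reporting to the Sponsor through the log remains. Separately, 11.3 contradicts 11.1 and 11.2 on which deaths reach the Sponsor.

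This rests on three assumptions: that intervention carries its Section 6.2 meaning, since no other is given; that the missing verb in the SAE definition is attributable or its equivalent; and that the Sponsor's procedure, which is not shown, does not override the protocol's own words. The contradiction on scope survives if the first assumption is relaxed to mean the study procedures. It would disappear only if 11.3 were expressly limited to immediate notification. No feasibility estimate or sample size is affected.

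**What to change.** 1. In Sections 11.1 and 11.3, replace the reference to the intervention with the study procedures, named as maternal, cord and infant blood sampling and the rectovaginal swab.
2. Complete the broken sentence in the SAE definition.
3. Reconcile 11.1 to 11.3 with 6.2 so that, for a death, the degree of causation required, the recipients and the time limit are stated once. Say whether 11.3 adds to the SAE report and the log or restricts them. Which causality rule and which time limit to adopt is for the Sponsor to decide.

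Cost: wording changes in Section 11 only. Design, sample size and data collection stay as they are.
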